5. SELECTION OF STUDY POPULATION AND WITHDRAWAL CRITERIA

Specific information regarding warnings, precautions, contraindications, adverse events, and other pertinent information on the GSK investigational product or other study treatment that may impact subject eligibility is provided in the Investigator's Brochure.

Deviations from inclusion and exclusion criteria are not allowed because they can potentially jeopardize the scientific integrity of the study, regulatory acceptability or subject safety. Therefore, adherence to the criteria as specified in the protocol is essential.

5.1. Inclusion Criteria

A subject will be eligible for inclusion in this study only if all of the following criteria apply:

AGE
1. ≥ 21 years of age at the time of signing the informed consent form

TYPE OF SUBJECT AND DIAGNOSIS INCLUDING DISEASE SEVERITY
2. Diagnosis of heart failure (New York Heart Association Class II-IV) for a minimum of 3 months prior to screening 3. Clinically stable with no changes in optimized guidance-directed medications and no hospitalizations for heart failure for at least 1 month prior to Screening 4. NT-proBNP >400 pg/mL measured within 6 months prior to OR at Screening 5. Average DLco measurements outside the normal range (% Predicted DLco $< 80\%$) during the Screening Period

WEIGHT
6. Body mass index (BMI) ≥ 18 and ≤ 45 kg/m ²

SEX

7. Male or female of non-childbearing potential

➤ Male patients with female partners of child bearing potential must comply with the following contraception requirements from the time of first dose of study medication until at least five half-lives of study medication OR for a cycle of spermatogenesis following five terminal half-lives after the last dose of study medication.

- a. Vasectomy with documentation of azoospermia.
- b. Male condom plus partner use of one of the contraceptive options below:
 - Contraceptive subdermal implant that meets the standard operating procedure (SOP) effectiveness criteria including a <1% rate of failure per year, as stated in the product label
 - Intrauterine device or intrauterine system that meets the SOP effectiveness criteria including a <1% rate of failure per year, as stated in the product label [Hatcher, 2007a]
 - Oral contraceptive, either combined or progestogen alone [Hatcher, 2007a]
 - Injectable progestogen [Hatcher, 2007a]
 - Contraceptive vaginal ring [Hatcher, 2007a]
 - Percutaneous contraceptive patches [Hatcher, 2007a]

These allowed methods of contraception are only effective when used consistently, correctly and in accordance with the product label. The investigator is responsible for ensuring that subjects understand how to properly use these methods of contraception.

➤ A female subject is eligible to participate if at least one of the following conditions applies:

- a. Non-reproductive potential defined as:
 - Pre-menopausal females with one of the following:
 - Documented tubal ligation
 - Documented hysteroscopic tubal occlusion procedure with follow-up confirmation of bilateral tubal occlusion
 - Hysterectomy
 - Documented bilateral oophorectomy
- b. Postmenopausal defined as 12 months of spontaneous amenorrhea. Females on hormone replacement therapy (HRT) and whose menopausal status is in doubt will be required to use one of the highly effective contraception methods if they wish to continue their HRT during the study. Otherwise, they must discontinue HRT to allow confirmation of post-menopausal status prior to study enrolment.

INFORMED CONSENT

8. Capable of giving signed informed consent which includes compliance with the requirements and restrictions listed in the consent form and in this protocol

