7.4.2. Pregnancy

- Details of all pregnancies in female partners of male subjects will be collected after the start of dosing and until the follow up visit.
- If a pregnancy is reported then the investigator should inform GSK within 2 weeks of learning of the pregnancy and should follow the procedures outlined in [Appendix 5](#).

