12.5. Appendix 5: Collection of Pregnancy Information

- Investigator will attempt to collect pregnancy information on any female partner of a male study subject who becomes pregnant while participating in this study. This applies only to subjects who are randomized to receive study medication.
- After obtaining the necessary signed informed consent from the female partner directly, the investigator will record pregnancy information on the appropriate form and submit it to GSK within 2 weeks of learning of the partner's pregnancy
- Partner will also be followed to determine the outcome of the pregnancy. Information on the status of the mother and child will be forwarded to GSK.
- Generally, follow-up will be no longer than 6 to 8 weeks following the estimated delivery date. Any termination of the pregnancy will be reported regardless of fetal status (presence or absence of anomalies) or indication for procedure.

[figure not shown]

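### Criterion 7b lets a woman on HRT with doubtful menopausal status enrol unconfirmed on contraception, with no pregnancy test scheduled and incomplete provision for a pregnancy in a female subject

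*Protocol*

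**What the plan says.** **Eligibility (Protocol 5.1, criterion 7).** The heading reads "Male or female of non-childbearing potential". A woman qualifies if either of two conditions holds. Part a covers documented sterilisation, hysterectomy or oophorectomy. Part b is "Postmenopausal defined as 12 months of spontaneous amenorrhea". Part b goes on to women taking HRT: a woman "whose menopausal status is in doubt will be required to use one of the highly effective contraception methods" if she wishes to remain on HRT during the study. If she does not take that course, the text says "they must discontinue HRT to allow confirmation of post-menopausal status prior to study enrolment".

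**Adherence (Protocol 5).** "Deviations from inclusion and exclusion criteria are not allowed".

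**Testing (Protocol 7.1 and Table 3).** The Time and Events Table, its 17 footnotes and Table 3 list no pregnancy test and no FSH. FSH appears in the current text only in the abbreviation list. A urine drug and alcohol test is scheduled at Screening and on Day -1 of each treatment period.

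**Pregnancy reporting.** The first bullet of 7.4.2 says "Details of all pregnancies in female partners of male subjects will be collected". The second bullet asks the investigator to tell the sponsor within 2 weeks once a pregnancy is reported and to follow Appendix 5. It does not say whose pregnancy. Appendix 5 concerns "pregnancy information on any female partner of a male study subject who becomes pregnant". Under it, once the partner has consented, "the investigator will record pregnancy information on the appropriate form and submit it to GSK within 2 weeks", and the partner is then followed to the outcome of the pregnancy.

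**The concern.** The heading and part b do not fit together. One says that women must be of non-childbearing potential. The other describes a woman for whom this is admittedly uncertain and offers her a way in that does not remove the uncertainty. Because Section 5 permits no deviations, sites will work from the wording as it stands.

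The rest of the protocol looks as though no female subject could be pregnant. Nothing scheduled would show whether a woman entering this way is pregnant before her first dose, and no exclusion criterion in 5.2 names pregnancy. The pregnancy procedures are written around the partners of male subjects, who take no study drug. At stake is the safety of a small number of women and any fetus exposed to the drug. No efficacy result is involved.

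**Working it through.** There is no figure in the plan to reproduce. The check sets the texts side by side and then does some simple counting.

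**Step 1. Ways in for a woman under criterion 7.**

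| Route | Status on entry | Confirmed before enrolment? | Pregnancy test scheduled? |
|---|---|---|---|
| Part a | Documented surgical or procedural infertility | Yes, for the procedures that must be documented | No |
| Part b, 12 months of amenorrhea, not in doubt | Meets the definition | By definition | No |
| Part b, in doubt, stops HRT | In doubt, then resolved | Yes, required | No |
| Part b, in doubt, continues HRT | In doubt | Not required | No |

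Only the last row conflicts with the heading. Confirmation is introduced by the word *otherwise*, which attaches it to stopping HRT and to nothing else.

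**Step 2. The other reading.** The HRT sentence could be an added precaution for women who already meet the 12-month definition. In that case a doubt about status, and a step to confirm it, would have little to do. The plain reading is the better one, but the text allows both, so two sites could apply it differently.

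**Step 3. Supporting detail.** The only list of contraceptive methods in criterion 7 is for partners of male patients. For men a start and stop time is given; for the woman continuing HRT none is. The stop-HRT route names no test or waiting time.

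**Step 4. Who the pregnancy text covers.**

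| Text | Partner of a male subject | Female subject |
|---|---|---|
| 7.4.2, first bullet (collection) | Yes | No |
| 7.4.2, second bullet (2-week notification) | Yes | Unclear: no person is named |
| Appendix 5 (form, 2-week submission) | Yes | No |
| Appendix 5 (follow-up to outcome) | Yes | No |

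For a female subject, notification is therefore ambiguous and outcome follow-up is absent. The second bullet sends the investigator to Appendix 5, which has no step written for her.

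**Step 5. Size.**

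- Possible exposure per affected woman: 7 dosing days + at least 5 days until the drug is undetectable = at least about 12 days. The 5 days come from the overdose text in 6.7; using them for ordinary dosing is an assumption.
- Rough bound on conception while on study: assume that the below-1%-per-year failure standard, which criterion 7 states for certain methods used by partners, also applies to these women. Over 12 days, 1% × 12/365 = 0.033%. Over the study's roughly 8 weeks (56 days), 1% × 56/365 = 0.153%.
- This bound does not cover a pregnancy already present on Day -1, which is what a pre-dose test would find. The documents give no figure for that.
- Tests needed if the route is kept: 1 per period × 2 periods = 2 per affected woman.
- Further enrolment: SAP 4.1 records that, after the prediction on 10 subjects, only one more patient would be enrolled. At most one future entrant could be affected.

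**The case against.** The strongest reply has four parts.

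**Reporting is not silent.** A reader might infer that a site has no duty to report a female subject's pregnancy within 2 weeks. The documents do not support that. The second bullet of 7.4.2 is not limited to partners on its face and can be read as covering any reported pregnancy. It can also be read as continuing the first bullet, so the fair description is ambiguity. The gap in Appendix 5's form and outcome follow-up remains.

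**There are other safeguards.** A reader might also infer that contraception is the only protection. That goes too far. Exclusion 12 allows the investigator or medical monitor to exclude an unsuitable woman, 5.5 allows withdrawal for safety, and 7.4 allows added safety tests. Open questioning about adverse events (7.4.1.2) might bring a pregnancy to light. A birth defect is an SAE (12.4.2), and a related SAE learned of after discharge must be notified (7.4.1.1). These are all real. But the first three are discretionary and none requires a pregnancy test. A birth defect would normally appear after the follow-up visit, when sites no longer have to seek events.

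**Continuing HRT on contraception is a legitimate clinical choice.** This stands. Removing the option would force HRT withdrawal on a woman who wants to take part. Amendment 1 made the changes requested in the FDA's IND review and lists none to part b; Amendment 2 carried part b forward unchanged. That does not show that the point was considered, but it gives no reason to call the option an error.

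**The numbers are negligible.** This also stands. No document shows that any such woman was enrolled, and the on-study conception bound is tiny.

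**Conclusion.** The point holds as a cheap safety improvement of very small magnitude. On its plain reading, part b admits a woman whose fertility has not been excluded, and no scheduled test checks whether she is pregnant before dosing. For a pregnancy in a female subject, 2-week notification is ambiguous and follow-up to outcome is not provided for.

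It does not follow that the HRT option must be deleted; that is a clinical decision for the sponsor. Nor do the documents show that any woman of childbearing potential has been dosed. The number affected is unknown and probably very small. Sample size, power and the DLco analysis are untouched.

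The conclusion rests on the plain reading of part b and on the protocol text alone. The Investigator's Brochure, consent form, laboratory manual and Study Reference Manual are not available here and may say more. Confidence is moderate for that reason.

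**What to change.** 1. **Add a test for women entering by the continue-HRT route only.** Run a urine pregnancy test on the urine already collected on Day -1 of each period, with the result known before dosing on Day 1 and a positive result stopping dosing. Both periods are needed because site staff, other than the pharmacist, do not know which period is active. A footnote to the Time and Events Table and a line in Table 3 are enough.
2. **Reword 7.4.2 and Appendix 5** so that collection, 2-week notification and follow-up to outcome cover pregnancies in female subjects as well as in partners of male subjects.

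If the sponsor prefers, removing the continue-HRT option would resolve the conflict with the heading instead. A woman of doubtful status would then have to stop HRT to take part, so this is optional.

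Cost: a short text change, two urine tests per affected woman on samples already taken, and slightly wider pregnancy collection. No endpoint or analysis changes.

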5.2. Exclusion Criteria

A subject will not be eligible for inclusion in this study if any of the following criteria apply:

CONCURRENT CONDITIONS/MEDICAL HISTORY (INCLUDES LIVER FUNCTION AND QTc INTERVAL)

1. History of acute coronary syndromes including unstable angina or myocardial infarction within 6 months of screening
2. Coronary revascularization including angioplasty and stenting within 6 months of Screening
3. History of stroke or seizure disorder within 5 years of Screening
4. Diagnosis of asthma
5. Diagnosis of chronic obstructive pulmonary disease (COPD) with $FEV_1 < 50\%$ of predicted measured within 4 weeks of Screening
6. History of a condition that required radiation therapy to the thorax
7. History of any type of malignancy within the past five years with the exception of successfully treated basal cell cancer of the skin
8. Active ulcer disease or gastrointestinal bleeding at the time of screening
9. Current or chronic history of liver disease, known hepatic impairment, or biliary abnormalities (with the exception of Gilbert's syndrome or asymptomatic gallstones)
10. Alanine transaminase (ALT) $>2\times$ Upper Limit of Normal (ULN) and bilirubin $>1.5\times$ ULN (isolated bilirubin $>1.5\times$ ULN is acceptable if bilirubin is fractionated and direct bilirubin $<35\%$)
11. QTc > 450 msec or QTc > 480 msec in subjects with Bundle Branch Block
 - The QTc is the QT interval corrected for heart rate according to Bazett's formula (QTcB), Fridericia's formula (QTcF), and/or another method, machine-read or manually over-read.
 - The *same* QT correction formula *must* be used for *each individual subject* throughout the study. This formula may not be changed or substituted once the subject has been enrolled.
 - For purposes of data analysis, QTcB, QTcF, another QT correction formula, or a composite of available values of QTc will be used as specified in the Reporting and Analysis Plan (RAP).
12. History or current evidence of any serious or clinically significant gastrointestinal, renal, endocrine, neurologic, hematologic or other condition that is uncontrolled on permitted therapies or that would, in the opinion of the investigator or the

CONCURRENT CONDITIONS/MEDICAL HISTORY (INCLUDES LIVER FUNCTION AND QTc INTERVAL)

GlaxoSmithKline (GSK) medical monitor, make the subject unsuitable for inclusion in this study

CONCOMITANT MEDICATIONS

13. Use of medications specified for the treatment of COPD including short- and long-acting bronchodilators (β -agonists and anticholinergics) and inhaled glucocorticoids as well as oxygen therapy
14. Use of a listed prohibited medication (Section [6.10.2](#)) within the restricted timeframe relative to the first dose of study medication
15. Use of a strong inhibitors or inducers of cytochrome P450 (CYP) 3A or p-glycoprotein (see Section [6.10.2](#))

RELEVANT HABITS

16. Current smoker
17. History of alcohol abuse within 6 months of the study in the opinion of the investigator(s).

CONTRAINdications

18. History of sensitivity to any of the study medications, or components thereof or a history of drug or other allergy that, in the opinion of the investigator or Medical Monitor, contraindicates their participation

DIAGNOSTIC ASSESSMENTS AND OTHER CRITERIA

19. Presence of hepatitis B surface antigen (HBsAg), positive hepatitis C antibody test result at screening or within 3 months of screening. For potent immunosuppressive agents, subjects with presence of hepatitis B core antibody (HBcAb) should also be excluded
20. A positive pre-study drug/alcohol screen (excluding prescribed medications)
21. Use of another investigational product in a clinical study within the following time period prior to the first administration of study medication in the current study: 30 days, 5 half-lives or twice the duration of the biological effect of the investigational product (whichever is longer)
22. Exposure to more than 4 investigational medicinal products within 12 months prior to the first administration of study medication

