5.5.1.1. Study Treatment Restart or Rechallenge

Study treatment restart or rechallenge after liver chemistry stopping criteria are met by any subject participating in this study is not allowed.

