12.2. Appendix 2: Liver Safety Required Actions and Follow up Assessments

Phase II liver chemistry stopping and increased monitoring criteria have been designed to assure subject safety and evaluate liver event etiology (in alignment with the FDA premarketing clinical liver safety guidance).

<http://www.fda.gov/downloads/Drugs/GuidanceComplianceRegulatoryInformation/Guidances/UCM174090.pdf>.

Phase II liver chemistry stopping criteria and required follow up assessments

Liver Chemistry Stopping Criteria – Liver Stopping Event	
ALT-absolute	ALT \geq 5xULN
ALT Increase	ALT \geq 3xULN persists for \geq 4 weeks
Bilirubin^{1,2}	ALT \geq 3xULN and bilirubin \geq 2xULN (>35% direct bilirubin)
INR²	ALT \geq 3xULN and INR>1.5, if INR measured
Cannot Monitor	ALT \geq 3xULN and cannot be monitored weekly for 4 weeks
Symptomatic³	ALT \geq 3xULN associated with symptoms (new or worsening) believed to be related to liver injury or hypersensitivity
Required Actions and Follow up Assessments following ANY Liver Stopping Event	
Actions	

 • Immediately discontinue study treatment • Report the event to GSK within 24 hours • Complete the liver event CRF and complete an SAE data collection tool if the event also meets the criteria for an SAE² • Perform liver event follow up assessments • Monitor the subject until liver chemistries resolve, stabilize, or return to within baseline (see MONITORING below) • Do not restart/rechallenge subject with study treatment unless allowed per protocol and GSK Medical Governance approval is granted • If restart/rechallenge not allowed per protocol or not granted, permanently discontinue study treatment and may continue subject in the study 	
 • Viral hepatitis serology⁴ • Blood sample for pharmacokinetic (PK) analysis, obtained 24 hours after last dose⁵ • Serum creatine phosphokinase (CPK) and lactate dehydrogenase (LDH). • Fractionate bilirubin, if total bilirubin \geq 2xULN • Obtain complete blood count with differential to assess eosinophilia • Record the appearance or worsening of clinical symptoms of liver injury, or hypersensitivity, on the AE report form • Record use of concomitant medications on the concomitant medications report

Liver Chemistry Stopping Criteria – Liver Stopping Event	

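### Exclusion criterion 10 joins its ALT and bilirubin limits with 'and', so its isolated-bilirubin exception is inert and no numeric entry limit excludes isolated ALT, even at the stopping level of 5x ULN

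*Protocol*

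**What the plan says.** Protocol 5.2 excludes a subject who meets any one of its criteria. Criterion 10 sets ALT >2x ULN and bilirubin >1.5x ULN, joined in the words "Upper Limit of Normal (ULN) and bilirubin". A parenthesis then says that isolated bilirubin >1.5x ULN "is acceptable if bilirubin is fractionated and direct bilirubin" is below 35%.

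Section 5 allows no deviations from the criteria and says that "adherence to the criteria as specified in the protocol is essential".

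Three other criteria bear on the liver:

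- Criterion 9 excludes "Current or chronic history of liver disease, known hepatic impairment, or biliary abnormalities", apart from Gilbert's syndrome and asymptomatic gallstones.
- Criterion 12 excludes uncontrolled serious conditions, and other conditions that in the opinion of the investigator or medical monitor would "make the subject unsuitable for inclusion in this study".
- Criterion 19 is serological: "Presence of hepatitis B surface antigen (HBsAg), positive hepatitis C antibody test result at screening" or within the 3 months around it.

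Appendix 2 (section 12.2) makes ALT >=5x ULN a liver stopping event by itself, with no bilirubin condition. The first required action is: "Immediately discontinue study treatment". Section 5.5.1.1 adds: "Study treatment restart or rechallenge after liver chemistry stopping criteria are met by any subject participating in this study is not allowed".

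**The concern.** An exception has a purpose only if the rule would otherwise catch the case that it spares. Under *and*, isolated bilirubin is never caught, so the parenthesis spares nobody. That is strong evidence that the criterion does not say what its author meant.

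The same connector leaves ALT alone without an entry limit. A subject can meet every numeric eligibility rule while at an ALT level at which the protocol forbids treatment. The protocol lists hepatic toxicity among its potential risks (section 4.6.1) and relies on serial liver enzymes to manage it, so the entry rule and the stopping rule should agree. What is at stake is subject safety at entry and consistent eligibility decisions. The SAP (section 8.1.2) refers to two sites. One that follows the literal text and one that follows the apparent intent would decide differently on the same subject.

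**Working it through.** The plan gives no figure to reproduce, so the check is one of logic.

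**Inputs.** From criterion 10: the ALT limit of 2x ULN, the bilirubin limit of 1.5x ULN, the direct-fraction limit of 35%, and the connector. From Appendix 2: the absolute stopping level of ALT >=5x ULN.

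**Definitions.** Let A = ALT/ULN, B = bilirubin/ULN and D = direct fraction.

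- Exception X: A <= 2, B > 1.5 and D < 35%.
- As written: excluded if (A > 2 and B > 1.5) and not X.
- With *or*: excluded if (A > 2 or B > 1.5) and not X.

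**Step 1: can the exception operate?** As written, it changes a decision only if A > 2 and A <= 2 both hold, which is impossible. With *or*, every subject in X meets B > 1.5, so the exception spares all of X.

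A grid confirms this. It has 101 ALT values (0 to 10x in steps of 0.1), 51 bilirubin values (0 to 5x in steps of 0.1) and 6 direct fractions (10, 20, 34, 35, 50 and 80%), giving 101 x 51 x 6 = 30,906 combinations. The exception changes the decision in 0 of them under *and*. Under *or* it changes 21 (ALT 0 to 2.0x) x 35 (bilirubin 1.6 to 5.0x) x 3 (direct fraction below 35%) = 2,205. These are grid points, not patients.

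**Step 2: which patterns are excluded by criterion 10?**

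| Pattern | As written | With *or* |
|---|---|---|
| 1a. ALT >2x to <5x, bilirubin <=1.5x | no | yes |
| 1b. ALT >=5x, bilirubin <=1.5x | no | yes |
| 2. ALT <=2x, bilirubin >1.5x, direct >=35% or not fractionated | no | yes |
| 3. ALT <=2x, bilirubin >1.5x, direct <35% | no | no (exception) |
| 4. ALT >2x and bilirubin >1.5x | yes | yes |

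The count is 1 of 5 as written and 4 of 5 with *or*. Three decisions change: 1b is the conflict with the stopping rule, 2 is the case that the parenthesis implies should be excluded, and 1a is the cost of the change.

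**Step 3: is there an ALT limit elsewhere?** Criterion 9 rests on history or diagnosis, criterion 12 mainly on control of the condition and judgement, and criterion 19 on hepatitis tests. None states an ALT value. SAP 11.7.1 flags ALT >=2x ULN, bilirubin >=1.5x ULN and the pair in separate rows. Those are reporting flags and do not govern entry, although they show that the sponsor treats each abnormality as a concern by itself.

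**Step 4: entry against stopping.** ALT of 5x ULN with bilirubin of 1.0x ULN is not excluded by any numeric criterion. The same ALT on treatment triggers immediate discontinuation with no restart. For ALT of 3x to <5x ULN there is no such conflict, because Appendix 2 lets treatment continue under weekly monitoring if bilirubin is <2x ULN and there are no related symptoms.

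**The case against.** The strongest reply is that the subject in question would rarely be enrolled. An unexplained ALT >=5x ULN could well be excluded under criterion 9 or 12, and a viral cause may be found under criterion 19. Liver enzymes are measured at Screening and again on Day -1, the investigator reviews laboratory safety (section 9.4.3), and clinically significant abnormal results during participation are to be repeated (section 7.4.9). This stands, and it limits the practical weight of the point. It does not supply the missing limit.

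A second reply is that *and* can be read as joining two list items, each excluding alone, and that section 5 bars waivers without settling how the word is read. A site may well read it that way. But that reading contradicts the literal connector, and it concedes that the text needs correcting.

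A third is that the 1-of-5 and 4-of-5 counts depend on how the patterns are divided. With 1a and 1b merged they become 1 of 4 and 3 of 4. That is correct. The counts show which decisions change, not how often.

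A reader might also infer that such a subject would be dosed until the next scheduled ALT on Day 4, because the Time and Events Table marks the eligibility check under Screening only. The documents do not support this. The Screening column runs from Day -25 to Day -1, and section 5.4 and Appendix 3 both have headings that refer to baseline failures, so Day -1 results are not clearly outside eligibility. Dosing would require both the Screening and the Day -1 result to go unacted on, which does not follow from criterion 10.

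**Conclusion.** The point holds as a defect of wording with a safety consequence. Read literally, criterion 10 excludes only the combined abnormality, its exception does nothing, and isolated ALT has no numeric entry limit even at the level that requires permanent discontinuation of treatment. This rests on reading *and* as a conjunction and on the absence of an ALT limit elsewhere in the eligibility criteria; the current protocol text supports both.

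The size is modest. The documents give no ALT distribution in this population, so the frequency cannot be calculated. It is probably low given the other safeguards. A reader might infer a loss of power or a biased estimate, since a subject stopped in Period I could not supply the two-period data that the SAP's Analysis Population requires. Without a frequency, no such effect can be derived and none is claimed. Nor do the documents show that 2.4 mg injures the liver: the hepatic findings listed are from rats at 300 mg/kg/day and one dog at 30 mg/kg/day. The wording should be corrected, but it does not undermine the trial.

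**What to change.** In criterion 10, replace *and* with *or* between the two limits and keep the parenthesis: ALT >2x ULN **or** bilirubin >1.5x ULN, with isolated bilirubin >1.5x ULN still accepted when it is fractionated and the direct fraction is <35%. The exception then operates, isolated bilirubin that is unfractionated or has a direct fraction of 35% or more is excluded, and nobody enters at or above the ALT stopping level.

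The cost is one word, made through a routine amendment with the usual ethics review, and a few additional screen failures. Their number is unknown. They would include subjects with isolated ALT >2x to <5x ULN, a wider group than the direct conflict at >=5x, but 2x ULN is the limit that the criterion already names.
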